6.9.3 Severity

Adverse events will be graded by the investigator according to severity:

- **Mild:** Symptom(s) barely noticeable to the patient and/or does not make the patient uncomfortable. The AE does not influence daily performance or functioning. Medical intervention is not ordinarily needed for relief of symptom(s).
- **Moderate:** Symptom(s) of a sufficient severity to make the patient uncomfortable. Performance of daily activities is influenced. Treatment of symptom(s) may be needed.
- **Severe:** Symptom(s) of a sufficient severity to cause the patient severe discomfort, and/or result in a marked impairment of function or may be even life threatening. Severity may cause cessation of treatment with LR769. Treatment for symptom(s) is given. The AE produces sequelae, which may also require (prolonged) treatment.

Note: Severe is not equivalent to serious.

6.9.4 Relationship

For all AEs, the investigator will be asked to record the drug relatedness of the event in the source documents and enter the data in the eCRF. For this assessment the investigator will need to take into account the time relationship between LR769 administration and the occurrence of the event, the expected pharmacology of LR769, the potential contribution of the underlying disease under investigation and/or any other concomitant diseases/medical history, evolution of the event when LR769 was withdrawn, and whether the event recurred after a re-challenge.

The relationship criteria include:

- *Unrelated* (event with a time to drug intake that makes a relationship unlikely and disease or other drugs provide a clear explanation; negative re-challenge)
- *Remote/unlikely* (event with a time to drug that makes a relationship improbable [but not impossible] and disease or other drugs provide plausible explanations)
- *Possibly* (event with reasonable time relationship to drug intake that could also be explained by disease or other drugs and information on drug withdrawal/re-challenge lacking or unclear)
- *Probably* (event occurred within reasonable time relationship to drug intake, is unlikely to be attributed to disease or other drugs and response to withdrawal)
- *Definitely* (event with plausible time relationship to drug intake which cannot be explained by disease or other drugs and/or plausible response to withdrawal and/or definitively pharmacologically plausible and/or positive re-challenge)

6.9.5 Expectedness

An AE is expected if the nature, severity, and outcome of the event are consistent with the reference safety information, ie, the [Investigator's Brochure](#).

6.9.6 Clinical Significance

Clinical significance is defined as any variation in physical/laboratory findings or AE that has medical consequences that result in an alteration in the patient's medical care.

6.9.7 Clinical Laboratory Adverse Events

Any change in laboratory value outside the normal range will be regarded as an AE if the investigator assesses the value as clinically significant. Changes in coagulation parameters expected in hemophilia patients are not regarded as AEs, unless they lead to clinical measures to prevent or treat any untoward events associated with this deviation of the parameter.

6.9.8 Serious Adverse Events

6.9.8.1 Definition

A serious adverse event (SAE) is defined by federal and international regulation as any AE occurring at any dose that results in any of the following outcomes: death, life-threatening AE, hospitalization or prolongation of existing hospitalization, a persistent or significant disability/incapacity, or a congenital anomaly/birth defect.

Important medical events that may not result in death, be life threatening, or require hospitalization may be considered an SAE when, based upon appropriate medical judgment, they may jeopardize the patient and may require medical or surgical intervention to prevent one of the outcomes listed in this definition. Examples of such medical events include allergic bronchospasm requiring intensive treatment in an emergency room or at home, blood dyscrasias or convulsions that do not result in inpatient hospitalization, or the development of drug dependency or drug abuse. Any suspected transmission via a medicinal product of an infectious agent is also considered a SAE.

6.9.8.2 Reporting Serious Adverse Events

The necessity and time requirements for reporting SAEs to the Sponsor or designee and regulatory agencies are as follows:

- All SAEs will be reported via the eCRF system within 24 hours of the investigator's first knowledge of the event, even if the event does not appear to be related to LR769. In case reporting via the eCRF is not available, the SAE may be reported via fax in order to meet the reporting requirements.

In case of failure of the eCRF reporting, SAE forms are to be directed to:

[contact] (country specific fax instructions will be provided where applicable)

- For all SAEs, a detailed written description that includes anonymized copies of available relevant patient records, autopsy reports, and other documents will be sent within 24 hours of the investigator's first knowledge of the SAE.
- SAEs that are life threatening or result in death, and are unexpected and related to LR769 will be reported to regulatory authorities within 7 days of receipt of the event. Any follow up to the initial SAE report will be submitted to regulatory authorities within 8 days of the initial report (ie, 15 days of receipt of the initial report).
- Any SAE that is unexpected and related to LR769, results in hospitalization or prolongs an existing hospitalization, results in persistent or significant disability/incapacity, or is a congenital anomaly/birth defect will be reported to regulatory authorities within 15 days of receipt of the report. Some regulatory authorities may have alternative timelines for submission of suspected unexpected serious adverse reactions. In those cases, specific local requirements for submission of SAE reports will be applied.
- All SAEs will be followed until resolution or stabilization. Follow-up reports for SAEs reported as 7- or 15-day reports will be submitted within the same time frame as the initial report.

Additionally, the IRB and/or Ethics Committee (EC) must be notified in writing of any unexpected, related SAEs or as required by the local IRB/EC. It is the responsibility of the investigator/contract research organization (CRO) to notify the IRB/EC.

If applicable, SAEs will be reported to the appropriate regulatory agencies by the Sponsor or designee. In case the local regulations require notification through the investigator, the Sponsor will facilitate this process.

6.9.9 Treatment-Emergent Adverse Events

All AEs that occur after the first administration of LR769 will be regarded as treatment emergent (TEAE). All AEs occurring from signing the Informed Consent up to the first administration of LR769 will also be collected and will be referred to as non-TEAEs. Adverse events that are present prior to the first administration of LR769 but subsequently worsen will be considered TEAEs.

A potential risk associated with the administration of LR769 is the occurrence of an allergic or anaphylactic type reaction to either the recombinant molecule or any of the potentially present host-related impurities. Specific emphasis will be put on the observation of the patient after initial administration of LR769 to detect the occurrence of any potential allergic reaction. Symptoms of such a reaction may consist of, but are not limited to:

- Skin redness, rash, hives

- Mucosal and/or skin swelling
- Difficulty breathing
- Hypotension
- Headache
- Dizziness
- Nausea

If any one or more of these symptoms occur, the responsible physician at the site will assess the patient and determine whether the symptoms are consistent with an acute allergic reaction and treat the symptoms accordingly.

Although reported to be rare in hemophilia patients, a potential risk associated with the administration of LR769 is an exaggerated PD action, leading to a thromboembolic event. Specific emphasis will be put on the observation of the patient directly after administration of LR769 as well as during the follow-up assessments to detect the occurrence of any thromboembolic events. Events that may occur are myocardial infarction, ischemic cerebrovascular accident, arterial thrombosis (eg, aorta, intestinal), DVT, and PE. In case signs and symptoms of any of these occur in the patients during the study, the responsible physician at the site will need to assess the symptoms and order and review diagnostic procedures (ECG, ultrasound, computed tomography [CT], magnetic resonance imaging [MRI], Doppler, D-dimer, etc) as appropriate to confirm or refute the diagnosis. In case of symptoms suggestive of a DVT or PE, the guidelines for diagnosis as published by the American College of Physicians ([Qaseem et al., 2007](#)) is suggested as guidance for determining the need for additional diagnostic tools.

If an acute allergic reaction or a confirmed thrombotic event occurs in association with the administration of the LR769, such event will be reported in the same manner and timelines as a SAE (see [Section 6.9.8.2](#)), even when it does not meet the criteria for seriousness as listed in [Section 6.9.8.1](#).

6.10 Surgical or Invasive Procedure Characteristics

The surgeon/practitioner will determine the following predicted surgical or invasive procedure characteristics and record them prior to the procedure:

- major or minor
- maximum expected blood loss in a patient without a bleeding disorder who is undergoing this type of procedure
- type of anesthesia

After the surgery or invasive procedure, the surgeon/practitioner will determine the actual characteristics of the procedure and record them:

- major or minor
- duration of procedure
- estimated blood loss
- factors that may have influenced bleeding independent of hemostasis, eg, surgical complications, difficulties owing to scarring, adhesions, problems with suturing vessels
- actual type of anesthesia
- complications

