6.8 Efficacy Assessments

Efficacy Assessments:

The intraoperative efficacy of LR769 will be assessed by the surgeon/practitioner; all other efficacy assessments will be made by the investigator or designee as specified in [Appendix 1](#). Assessments for major and minor procedures will be performed at the same timepoints.

The final assessment (which represents the primary efficacy outcome) will be performed by the investigator at the study center 48 (± 4) hours after the last dose of LR769 and will be based upon the totality of the assessments performed on the patient at each timepoint, also taking into consideration the number of (interventions for) bleeding episodes, oozing, blood transfusions, and the total amount of LR769 used.

All efficacy assessments will be recorded in the patient's source records and on the eCRF.

Intraoperative Assessment of Efficacy by Surgeon/Practitioner

The surgeon/practitioner's rating of intraoperative efficacy of LR769 will be based on the following parameters:

- Estimated blood loss in the surgical patient as compared to the maximum expected volume of blood loss in a patient without a bleeding disorder:
 - Prior to surgery, the surgeon will note if the procedure is major or minor and the type of anesthesia that is planned, and estimate the maximum expected volume of blood loss based upon the type of surgery and the surgeon/practitioner's previous experience in a patient who does not have a bleeding disorder. After the procedure, the surgeon/practitioner will determine the actual characteristics of the procedure and estimate the volume of blood lost during the procedure using the following factors as a guide: volume of drainage fluid, volume of fluid on sponges and towels, fluid replacement given, transfusion requirements, etc. The maximum expected volume of blood loss and the estimated volume of blood loss during the procedure will be recorded.
 - The surgeon/practitioner will assess the intraoperative hemostasis by comparing the estimated intraoperative blood loss with the maximum expected blood loss estimated prior to the procedure as well as the amount of fluid replacement given, transfusion requirements, hemodynamic stability, etc

Comments from the surgeon/practitioner may be necessary if extenuating circumstances occurred (eg, an artery was briefly severed and required additional time for surgical control of the bleeding creating a larger than expected blood loss.

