Taking into account the above parameters, the intraoperative response to treatment will be rated as follows:

- Excellent: intraoperative blood loss similar to or less than expected for this type of procedure in a patient who does not have a bleeding disorder and who is undergoing the same surgical or other invasive procedure; no blood component transfusion is required
- Good: intraoperative blood loss that is greater than expected (but not more than 50% greater) for this type of procedure in a patient who does not have a bleeding disorder and who is undergoing the same surgical or other invasive procedure; no unexpected increased blood component transfusion requirement
- Moderate: intraoperative blood loss that is substantially greater than expected (more than 50% greater) for this type of procedure in a patient who does not have a bleeding disorder and who is undergoing the same surgical or other invasive procedure, not explained by a surgical/medical issue other than hemophilia; additional blood component (within 2-fold greater than expected) transfusion is necessary
- Poor: uncontrolled intraoperative blood loss, not explained by a surgical/medical issue other than hemophilia, that requires intervention (rescue therapy requirement [bypass agent or porcine FVIII], and/or increased blood component [>2 -fold greater than expected] transfusion, and/or leads to hypotension or unexpected transfer to Intensive Care Unit [ICU])

Investigator or Designee Assessment of Hemostasis on Postoperative Days

- Excellent: postoperative blood loss similar to or less than expected following this type of procedure in a patient who does not have a bleeding disorder and who is undergoing the same surgical or other invasive procedure; no blood component transfusion is required
- Good: postoperative blood loss greater than expected following this type of procedure in a patient who does not have a bleeding disorder and who is undergoing the same surgical or other invasive procedure, not explained by a surgical/medical issue other than hemophilia; no unexpected need for blood component transfusion

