- Moderate: postoperative blood loss that is substantially greater than expected following this type of procedure in a patient who does not have a bleeding disorder and who is undergoing the same surgical or other invasive procedure, not explained by a surgical/medical issue other than hemophilia; additional blood component [within 2-fold greater than expected] transfusion is necessary
- Poor: uncontrolled postoperative blood loss, not explained by a surgical/medical issue other than hemophilia that requires intervention (rescue therapy requirement [bypass agent or porcine FVIII], and/or increased blood component [>2 -fold greater than expected] transfusion, and/or leads to hypotension or unexpected transfer to Intensive Care Unit [ICU])

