Appendix 1 Schedule of Events

Evaluation	Screening Days -21 to -1	Procedures + LR769 Treatment						Follow-Up Visits		
		Pre Procedure	Immediately Postoperative	24 (±2) hrs after procedure completion	Every 24 (±2) hrs after procedure completion	7-14 days after 1 st dose of LR769 ⁹	Last Dose of LR769	Early Termination	48 (±4) hrs after last dose	28 (±3) days after last dose
Informed Consent	X									
Inclusion/Exclusion Criteria	X	X								
Demographics and Detailed Medical History	X									
Physical Examination ¹	X	X ⁸						X	X	
Safety Lab Tests										
Hematology, chemistry, urinalysis (local lab)	X			X				X	X	X
Coagulation ¹⁰ , serology ¹²	X									
LR769 Administration ²		X								
Surgical/Invasive Procedure Characteristics ³		X	X							
Postoperative Assessment ⁴				X	X		X	X	X	
Vital Signs ⁵	X	X		X				X	X	
12-Lead ECG	X									

Evaluation	Screening Days -21 to -1	Procedures + LR769 Treatment						Follow-Up Visits		
		Pre Procedure	Immediately Postoperative	24 (±2) hrs after procedure completion	Every 24 (±2) hrs after procedure completion	7-14 days after 1 st dose of LR769 ⁹	Last Dose of LR769	Early Termination	48 (±4) hrs after last dose	28 (±3) days after last dose
Efficacy Assessments ⁶										
Surgeon's Assessment			X							
Investigator's Assessment				X	X		X	X	X	
Adverse Event Assessment	X	X ¹⁰								
Concomitant Medication	X	X								
Immunogenicity		X ⁷				X ⁹		X ⁷	X	X ⁷

¹ Height will be measured at screening only.

² Initial dose of 75 µg/kg (minor surgery or other minor invasive procedure) or 200 µg/kg (major surgery or other major invasive procedure) of LR769 will be administered as an IV bolus dose within ≤2 minutes prior to surgical incision or start of the invasive procedure; subsequent doses of 75 µg/kg of LR769 will be administered as an IV bolus dose of LR769 within ≤2 minutes during and after surgical or other invasive procedure; duration of treatment will be dependent on the type of procedure and the patient's status in accordance with [Table 1](#) and [Table 2](#).

³ Surgical/invasive procedure characteristics: Predicted surgery/invasive procedure characteristics: major or minor, maximum expected blood loss in a patient without hemophilia, type of anesthesia. Actual surgery/invasive procedure characteristics: major or minor, duration, estimated blood loss, factors that may have influenced bleeding independent of hemostasis, actual type of anesthesia, and complications.

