7.6.3 Surgery Characteristics

Surgery characteristics will be summarized by type of surgery and overall. The following characteristics will be included in the summary: predicted type (major or minor), predicted maximum blood loss in a patient without a bleeding disorder who is

undergoing this type of procedure, predicted anesthesia, actual type (major or minor), estimated actual blood loss, actual anesthesia, and surgery complications.

Listing of surgery characteristics will be created.

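### The plan does not require expected postoperative blood loss or expected transfusion to be recorded before the procedure, although the success line of the primary endpoint refers to both

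*Protocol*

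**What the plan says.** **Recorded before surgery.** Protocol 6.10 has the surgeon or practitioner "determine the following predicted surgical or invasive procedure characteristics and record them prior to the procedure". There are three items: major or minor, the "maximum expected blood loss in a patient without a bleeding disorder who is undergoing this type of procedure", and the type of anesthesia. Appendix 1, footnote 3, gives the same list: "major or minor, maximum expected blood loss in a patient without hemophilia, type of anesthesia". Protocol 7.2.1 calls for the predicted characteristics without adding any. SAP 7.6.3 summarizes the same items, including the "predicted maximum blood loss in a patient without a bleeding disorder who is" having that procedure.

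**Use of that reference.** In 6.8 the surgeon rates intraoperative hemostasis by "comparing the estimated intraoperative blood loss with the maximum expected blood loss estimated prior to the procedure", together with fluids, transfusion and hemodynamic stability.

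**The primary endpoint.** Protocol 9.5.1 and SAP 7.7.1 take the percentage of procedures that the investigator rates Good or Excellent 48 (±4) hours after the last dose. The postoperative scale is in 6.8:
- The lowest success grade begins "Good: postoperative blood loss greater than expected following this type of procedure in a patient who does not have a bleeding disorder" and adds "no unexpected need for blood component transfusion".
- The highest failure grade, Moderate, needs substantially greater loss than expected that is not otherwise explained, and "additional blood component [within 2-fold greater than expected] transfusion is necessary".

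**Design.** The study has one arm (3.2) and blinding is not applicable (5.4). Neither document describes independent adjudication of the ratings.

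**The concern.** Without a control arm, the word expected does the work of a comparator. If its value is first formed when the rating is made, by someone who knows the treatment and has seen how much the patient bled and was transfused, the comparator can move with the outcome. This need not be deliberate: a transfusion that has already been given is easily regarded as usual for that operation.

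The protocol accepts this reasoning for intraoperative loss, since it has the surgeon commit to a figure beforehand. It does not extend the safeguard to the scale that produces the primary endpoint. At stake is how far a reader can trust a success percentage based on about a dozen procedures.

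**Working it through.** The plan states no figure to reproduce. The sample size is a minimum agreed with authorities (9.2), with no null rate, target rate or power. The check therefore sets what is recorded beside what the scales need.

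**Step 1. Expectations used and expectations recorded**

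| Expectation the rating needs | Where it is used (6.8) | Required in advance? |
|---|---|---|
| Intraoperative blood loss | Surgeon's rating, with a 50% cut between Good and Moderate | Yes (6.10; Appendix 1, footnote 3) |
| Postoperative blood loss | Investigator's rating; greater versus substantially greater, no number | No |
| Transfusion need | Both scales: unexpected, additional, within or above 2-fold | No |

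Section 6.10 does not itself call its blood-loss item intraoperative. That limit comes from 6.8 and the synopsis, which pair it with blood lost during the procedure. Even if it were read as covering the whole perioperative period, one maximum volume gives no transfusion expectation.

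**Step 2. Which boundaries affect the primary endpoint**

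- Excellent versus Good: both count as success, so the primary does not change.
- Good versus Moderate: this is the success/failure line. It uses expected postoperative loss and whether transfusion was unexpected or additional, so the primary depends on the unrecorded expectations here.
- Moderate versus Poor: this uses the 2-fold transfusion rule, which also lacks a recorded base amount. Both grades are failures, so only the secondary four-category distribution is affected.

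**Step 3. Illustration of sensitivity**

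Inputs: at least 12 procedures, of which at least 6 are major (3.3), and a Clopper-Pearson 95% interval (9.5.1). For x successes in n, the lower limit is the 0.025 quantile of Beta(x, n − x + 1). When x = n this is 0.025^(1/n).

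- 12/12: 0.025^(1/12) = 73.5%. 11/12: the quantile of Beta(11, 2) is 61.5%. The estimate moves by 1/12 = 8.3 points and the lower limit by 73.5 − 61.5 = 12.0 points.
- 6/6 major: 0.025^(1/6) = 54.1%. 5/6: the quantile of Beta(5, 2) is 35.9%. The estimate moves by 1/6 = 16.7 points.

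These are the effects of any one changed rating, whatever its cause. They do not estimate how often the expectation would decide a rating, and the documents give no basis for such an estimate.

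**The case against.** Several points on the other side have force.

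- **The primary is partly anchored.** The synopsis, 9.5.1 and SAP 7.7.1 require the final rating to consider the surgeon's intraoperative assessment, which has a loss reference set in advance. A reader might infer that the primary has no prior reference at all; that would be wrong. The gap concerns postoperative loss and transfusion.
- **Transfusion alone does not decide the grade.** A reader might infer that calling a transfusion expected or unexpected is enough to switch Good to Moderate. The wording does not support this, because Moderate also needs substantially greater loss that is not explained by something other than hemophilia. That loss criterion is itself judged against an unrecorded expectation, so the gap remains, but in a less simple form.
- **The record is not empty.** Blood products are captured with date, time, type and amount (5.5, 6.11). Hemoglobin change, bleeding episodes and re-explorations are secondary endpoints. Ratings are made every 24 (±2) hours during treatment. A reader can use these to question a rating, but they show what happened and not what was expected.
- **The eCRF is not available.** SAP section 1 cites one dated 25 July 2016, and it may contain these fields. The finding is that the protocol and SAP do not require them.
- **No formal decision depends on the rate.** Efficacy is descriptive, with no threshold or test. This limits the consequence but does not remove the value of a fixed reference.

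**Conclusion.** The point holds in a limited form. The protocol and SAP leave two expectations behind the postoperative scale, blood loss and transfusion, without any requirement to record them beforehand. Both bear on the Good/Moderate line that defines primary success, and the rater is the unblinded treating investigator.

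The documents show that the reference could be set afterwards. They do not show that it was or will be, and they do not support reading 8.3 or 16.7 points as the size of a bias. Those figures assume the minimum numbers of procedures, a starting point of no failures and exactly one changed rating. This is a worthwhile low-cost improvement and does not by itself invalidate the endpoint.

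**What to change.** 1. Add to the pre-procedure items in 6.10, 7.2.1 and Appendix 1, footnote 3 (and to the eCRF if not already there) two entries by the surgeon or practitioner, completed before the first LR769 dose and referring to a patient without a bleeding disorder having the same procedure: (a) expected postoperative blood loss or drain output; (b) expected blood-component transfusion by type and units, intraoperative and postoperative.
2. State in 6.8 that expected, unexpected and 2-fold greater than expected refer to these recorded values.
3. In the SAP, list predicted and actual values beside each primary rating.

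The cost is two more entries on a form the surgeon already completes, a short amendment and one listing. Sample size, treatment and the interval method do not change.

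The remedy is incomplete in two respects. A surgeon's forecast is approximate, as the existing blood-loss forecast is. Some subjectivity also remains, because greater versus substantially greater postoperative loss has no numeric cut, unlike the 50% on the intraoperative scale.
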